6.3.1. Imputation of Partial Dates

6.3.1.1. TEAE Status When Start Date and Time Is Unknown

The following rules will apply in cases where start date of an AE is unknown:

- If the AE onset date and time is unknown and the end date and time is after the date and time of the first dosing date or ongoing, then the AE will be considered a TEAE.
- If the AE onset date and time is unknown and the end date and time is before the date and time of the first dosing date, then the AE will not be considered a TEAE.
- If both the start date and time and end date and time are unknown (or ongoing), then the AE will be considered a TEAE, following the worst-case principle.

6.3.1.2. Concomitant Status of Medication for Completely/Partial Unknown Start Date

The following rules will apply in cases where the start date of concomitant medication is completely unknown:

- If the medication onset date is unknown and the end date is on or after the informed consent date or medication is ongoing, then the medication will be considered as concomitant.
- If the medication onset date is unknown and the end date is before the informed consent date, then the medication will not be considered as concomitant.
- If both the start and end dates are unknown, then the medication will be considered as concomitant. This approach is considered to be the most conservative following the worst-case principle.
- If the medication onset date is partly present and month/year is before informed consent date, then the medication will not be considered as concomitant.

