4.3. Prior/Concomitant Medications

All medications will be coded using the World Health Organization (WHO) Drug Dictionary. The version of the dictionary will be defined in the Data Management Plan (DMP).

A prior medication is any medication taken within 90 days prior to the Screening Visit.

A concomitant medication is defined as any medication taken from the Screening Visit through the Day 28 Post-surgery follow-up visit/EOS/ET Visit or the medication is reported as ongoing.

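### SAP 6.3.1.2 labels a drug with a partial pre-consent start date as not concomitant even when it is ongoing or ended after consent, against SAP 4.3 and protocol 6.6

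*SAP*

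**What the plan says.** SAP 4.3 counts a drug as concomitant if it is used at any time between Screening and the last study visit, and adds the clause "or the medication is reported as ongoing". The same section says: "A prior medication is any medication taken within 90 days prior to the Screening Visit". A drug can therefore be both prior and concomitant. Protocol 6.6 uses the same two windows, 90 days before Screening and Screening through Day 28 or early termination.

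SAP 6.3.1.2 then gives four rules for incomplete start dates. Three are for a start date that is wholly unknown:

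- If the drug ended on or after consent, or is ongoing, it is concomitant: "end date is on or after the informed consent date or medication is ongoing, then the medication will be considered as concomitant".
- If it ended before consent, it is not.
- If both dates are unknown, it is concomitant, and the SAP gives its reason: "This approach is considered to be the most conservative following the worst-case principle".

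The fourth rule is for a partial start date: "If the medication onset date is partly present and month/year is before informed consent date, then the medication will not be considered as concomitant". The section heading covers partial and complete absence of the start date, but the sentence that introduces the list mentions only a completely unknown start.

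SAP 7.5 plans listings of prior and concomitant medications for all subjects and no summary table. SAP 6.1 commits to listing all CRF data and derived variables.

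**The concern.** Whether a drug is concomitant depends on whether it was taken during the study. A start month before consent does not answer that; the end date or ongoing status does. The first three rules use that information and the fourth ignores it. More information about the start date can then produce a worse answer: an ongoing drug with no start date at all is labelled correctly, and the same drug with a known earlier month is not.

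What is at stake is the accuracy of a derived label. Medications are reported only through listings, and 8 to 10 subjects are planned, so a wrong label sits in front of the reader with no summary to dilute it. A programmer who follows 6.3.1.2 literally will produce a flag that breaks the definition in 4.3. One who follows 4.3 will produce a different flag from the same data.

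**Working it through.** The plan states no figure here, so the check is one of logic. The definition in SAP 4.3 and the rules in SAP 6.3.1.2 were compared for each kind of start date and each end status.

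Inputs:

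- Definition (SAP 4.3; protocol 6.6 has the same window): concomitant if taken from Screening on, or ongoing.
- Rules (SAP 6.3.1.2): as set out above. A complete start date has no rule there, so the definition applies directly.
- Assumption: the consent date and the Screening Visit are treated as the same point in time. Protocol 10.1.3 and the Schedule of Activities place consent at Screening.
- Dates for illustration only: consent on 15 January 2020, with an end date of 20 February 2020 (after consent) or 5 January 2020 (before consent).

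| Start date | End status | SAP 4.3 definition | SAP 6.3.1.2 rule |
|---|---|---|---|
| Complete, before consent | Ongoing | Concomitant | (4.3 applies) Concomitant |
| Complete, before consent | Ended after consent | Concomitant | (4.3 applies) Concomitant |
| Complete, before consent | Ended before consent | Not | (4.3 applies) Not |
| Complete, before consent | Unknown | Undetermined | No rule |
| Partial, before consent | Ongoing | Concomitant | **Not** |
| Partial, before consent | Ended after consent | Concomitant | **Not** |
| Partial, before consent | Ended before consent | Not | Not |
| Partial, before consent | Unknown | Undetermined | Not |
| Wholly unknown | Ongoing | Concomitant | Concomitant |
| Wholly unknown | Ended after consent | Concomitant | Concomitant |
| Wholly unknown | Ended before consent | Not | Not |
| Wholly unknown | Unknown | Undetermined | Concomitant |

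Of the 12 combinations, the definition settles 9. Rule and definition agree in 7 of those 9. The 2 disagreements are both in the partial-start block: ongoing, and ended after consent.

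The partial start with an unknown end is a separate case. The definition cannot settle it, so a default is needed. With both dates missing, the SAP defaults to concomitant and gives the worst case as its reason. With an earlier start month known and the end still missing, it defaults the other way. The known start month says nothing about when use stopped, so it gives no reason to reverse the default.

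With the fourth rule made conditional on the end date, the two mismatched rows agree with 4.3, and the unknown-end row follows the default used when both dates are missing.

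**The case against.** Three arguments can be made in the plan's defence.

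First, the text may never bite. SAP 4.3 already settles any drug recorded as ongoing ("or the medication is reported as ongoing"), and the lead-in to 6.3.1.2 limits the list to wholly unknown start dates. A programmer might apply 4.3 first and not reach the fourth rule. This stands as far as it goes: it is not certain that every affected drug will be mislabelled. It does not rescue the text. The fourth rule is explicit, the section heading includes partial dates, and a specific rule is naturally read as governing the case it names. SAP section 8 declares no planned change from the protocol, which points to a drafting slip.

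Second, nothing is lost. This stands. A drug started before consent and taken continuously into the study was also in use in the 90 days before Screening, so it qualifies as prior and is listed with its recorded dates. All CRF data are listed in any case. A reader might infer that long-term drugs vanish from the outputs, but the documents do not support that. Drugs with a complete start date are unaffected, drugs that ended before consent are labelled correctly, and the layout of the listings is in SAP Module 2, which is not among the documents.

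Third, no result depends on the label. This also stands. No hypothesis test is planned, and the primary comparison is of dosed tissue with the same subject's undosed control. A reader might infer that a mislabelled drug, such as the low-dose aspirin the plan permits, could change how a subject's bruising is read. Nothing in the documents links the concomitant flag to the pathology reading or the narratives. Nor do they show that detection of prohibited-medication deviations depends on the flag; protocol 6.6.1 has such use recorded and reported to the medical monitor separately.

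**Conclusion.** The fourth rule of SAP 6.3.1.2 is wrong as written. For a drug with a partial pre-consent start that is ongoing or ended after consent, it contradicts SAP 4.3 and protocol 6.6. For one with an unknown end date, it reverses the SAP's own default. No other section corrects it.

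The consequence is small: a wrong prior/concomitant label in a listing, for drugs with partial start dates only. The number of drugs affected cannot be estimated, because the documents give no frequency of partial dates.

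The conclusion rests on two assumptions: that consent and Screening coincide, and that the worst-case reasoning given for two missing dates is meant to carry over to a partial start with a missing end. The second bears only on the unknown-end case; the two direct contradictions do not need it.

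**What to change.** Replace the fourth rule of SAP 6.3.1.2 with one that depends on the end date. A medication with a partial start date before consent is not concomitant only if its end date is before consent. It is concomitant if it is ongoing, ended on or after consent, or has an unknown end date. Amend the lead-in so that the list covers partial as well as completely unknown start dates.

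This costs about two sentences in the SAP and one line in the derivation program. It needs no new data and has no evident downside.

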7. STATISTICAL ANALYSES

7.1. Subject Disposition

The number and percent of subjects screened, screen failed and enrolled will be summarized. The numbers and percentages of subjects who complete and discontinue from the study will be summarized for overall subjects. For subjects who discontinue from the study, the reason for discontinuation will be tabulated. The number of subjects included in each study population and in each group will be summarized for overall as well.

Subjects excluded from the Safety Population or Evaluable Population will be listed.

A listing of disposition for all subjects will be provided. Screen failure reasons will also be listed. In addition, a listing for inclusion/ exclusion criteria will also be presented.

7.2. Protocol Deviations

Protocol deviations will not be summarized. A listing of all protocol deviations will be presented.

7.3. Demographics and Baseline Characteristics

Demographic and baseline characteristics, including age, sex, race, height, weight, and BMI will be summarized using appropriate descriptive statistics in Safety Population and Evaluable Population. If both the populations are identical, duplicate tables will not be produced.

Age, height (at screening), body weight (at screening) and BMI in kg/m² will be summarized as continuous variables using descriptive statistics.

Gender and race will be summarized as categorical variables using frequency counts and percentages.

History of tobacco and alcohol use will be summarized using frequency count and percent as:

- Alcohol use (Never, Current or Former)
- Tobacco use (Never, Current or Former)

All demographic and baseline characteristics will be presented in a listing for all subjects.

7.4. Medical History

Medical history will be recorded for each subject and will be coded using MedDRA. All medical and surgical history will be presented in a listing for all subjects.

7.5. Prior and Concomitant Medications/Procedures

All medications will be coded using the World Health Organization (WHO) Drug Dictionary. Listings of prior and concomitant medications/procedures will be presented for all subjects.

7.6. Abdominoplasty Procedure

Listings with details of the abdominoplasty surgery and date of surgery will be presented for all subjects. The histopathology data of the 2 subjects whose abdominoplasty surgery was delayed due to COVID-19 will be flagged in the listing.

7.7. Digital Photography

Subject listings will be presented with date of digital photographs taken, start time of photo session, and reasons if the digital photographs were not done per protocol.

7.8. Medical Clearance for Surgery

Listings with details of the medical clearance test for surgery (ie, whether pre-op testing was completed, and whether medical clearance was given to proceed with abdominoplasty surgery) and date of medical clearance will be presented for all subjects.

7.9. Safety Analyses

Safety data listings will be presented using the Safety Population.

7.9.1. Study Drug Exposure

A listing of CCH administration with details of start/end date/time of CCH administration along with the reasons for injections not given per protocol will be provided.

7.9.2. Adverse Events

Subject listings of all AEs, SAEs, AEs leading to study discontinuation, AEs resulting in drug interruption/withdrawn, AEs resulting in death, AESIs and AEs related to abdominoplasty will be provided.

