9.3. Statistical Hypotheses and Analyses

No statistical hypotheses and analyses are planned for the study. Subject narratives will be developed based on the histopathology and immunohistochemistry reports and safety data listings.

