9.3.2.1. Adverse Events

AEs will be coded using Medical Dictionary for Regulatory Activities (MedDRA) by preferred term within system organ class. The number of AEs and the number of subjects reporting AEs will be listed and summarized descriptively by body system, preferred term, severity, and causality. By-subject listings of AEs will be provided.

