9.3.2.2. Vital Signs

By-subject listings of vital signs will be provided.

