9.3.2.3. Immunogenicity

Samples from Screening will be analyzed for anti-AUX-I and anti-AUX-II antibodies. Samples from Day 0 and Follow-up/End of Study visits will be analyzed for anti-AUX-I antibodies, anti-AUX-II antibodies, and neutralizing antibodies. Neutralizing antibodies will only be tested from anti-drug antibody (ADA) positive subjects. By-subject listings of anti-AUX-I and anti-AUX-II antibody levels, and neutralizing antibody results (positive/negative) will be provided.

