5. ANALYSIS POPULATIONS

The study will use the following analyses population for data summarization:

Table 4: Analysis Population

Population	Definition	Displays
Evaluable Population	The Evaluable Population is defined as all subjects who receive at least 1 injection of study drug and have histopathology and immunohistochemistry results. The histopathology data of the 2 subjects whose abdominoplasty surgery was delayed due to COVID-19, will be analyzed separately.	This population will be used for summarization of demographic and baseline characteristics.
Safety Population	The Safety Population is defined as all subjects who receive at least 1 injection of study drug.	This population will be used for all analyses of subject disposition, demographic and baseline characteristics and safety data listings.

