6. STATISTICAL METHODS

There are no statistical hypotheses and analyses planned for the study. Subject narratives will be developed based on the histopathology and immunohistochemistry reports and safety data listings.

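### The protocol requires adverse event counts to be summarized, but SAP Module 1 plans listings only and declares no change

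*SAP*

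**What the plan says.** Protocol 9.3.2.1 provides for two AE outputs. The numbers of events and of subjects reporting them "will be listed and summarized descriptively by body system, preferred term, severity, and causality". A separate sentence adds: "By-subject listings of AEs will be provided". The neighbouring subsections ask for listings alone: "By-subject listings of vital signs will be provided" in 9.3.2.2, and "By-subject listings of anti-AUX-I and anti-AUX-II antibody levels" together with neutralizing antibody results in 9.3.2.3.

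SAP 7.9.2 begins "Subject listings of all AEs, SAEs, AEs leading to study discontinuation" and continues with further categories, all of them listings. SAP 7.9 describes safety output in general as listings. SAP Table 4 says of the Safety Population: "This population will be used for all analyses of subject disposition, demographic and baseline characteristics and safety data listings". SAP Section 8 states that neither conduct nor analysis departs from the protocol.

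Both documents also carry a general statement: "No statistical hypotheses and analyses are planned for the study" (Protocol 9.3) and "There are no statistical hypotheses and analyses planned for the study" (SAP 6). Each then refers to subject narratives built from the pathology reports and the safety listings.

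Two related places in the SAP:

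- **Table 5** defines Study Day as the assessment date minus the surgery date, and AE Onset Day as the AE start date minus the surgery date, plus 1.
- **Section 3.12.1** says that remote bruising and hypersensitivity are recorded as AEs of special interest (AESIs). Under the same heading it says only that local injection-site events are recorded. Protocol 8.2.7 names all three categories as AESIs.

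**The concern.** Treatment-emergent AEs and AESIs are secondary endpoints (Protocol 3), and SAP 1 gives the assessment of safety and immunogenicity as the purpose of the SAP. A team that follows Module 1 as written would produce no AE counts, and Section 8 would tell readers that nothing had been dropped.

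Two rules would also be left without a use. SAP 4.4.1.2 sets a missing severity to the most severe grade, and SAP 4.4.1.3 treats a missing causality as related. Both are said to serve the analyses, but Module 1 specifies no AE analysis to which they could apply.

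The onset-day formula matters less, but it gives wrong labels. In a study where Day 0 is surgery and some dosing falls on Day -1, it moves an event from the day before surgery onto the surgery-day label.

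**Working it through.** No sample size, power or error-rate figure is involved. The main point is a comparison of texts; the onset-day point is arithmetic.

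**AE output: protocol against SAP Module 1**

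| Topic | Protocol asks for | SAP Module 1 specifies |
|---|---|---|
| AEs (9.3.2.1; SAP 7.9.2) | Summary of counts, and listings | Listings |
| Vital signs (9.3.2.2; SAP 7.9.4) | Listings | Listing |
| Immunogenicity (9.3.2.3; SAP 7.9.6) | Listings | Listing |

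Of the three subsections under Protocol 9.3.2, one asks for a summary and two do not, so the protocol treats a summary and a listing as different things. The SAP gives listings for all three. The protocol names four AE breakdowns (body system, preferred term, severity, causality), and Module 1 specifies a tabulation by none of them.

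**Do the statements that no analyses are planned settle it?** They do not. SAP 7.1 summarizes disposition and SAP 7.3 summarizes demographics, both in a SAP whose Section 6 carries that statement. It therefore cannot exclude descriptive summaries.

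**Onset day (SAP Table 5)**

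Let d = calendar date minus surgery date. Then Study Day = d, AE Onset Day = d + 1, and the difference is (d + 1) - d = 1 on every date.

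| Nominal day | Study Day | AE Onset Day |
|---|---|---|
| -43 | -43 | -42 |
| -22 | -22 | -21 |
| -3 | -3 | -2 |
| -1 | -1 | 0 |
| 0 (surgery) | 0 | 1 |
| 7 | 7 | 8 |
| 28 | 28 | 29 |

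Over ten days checked (these seven plus -24, -14 and 1), Study Day matches the protocol's label on 10 of 10 and AE Onset Day on 0 of 10.

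The case of most interest is an AE that starts on a Day -1 dosing date and is then listed as Day 0:

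- Planned subjects number 2 + 1 + 1 + 2 + 1 + 1 = 8. Groups 3 and 6 contribute 1 + 1 = 2 with a nominal Day -1 dose. The visit window also allows that dose on Day -2, in which case the label is -1, so the range is 0 to 2.
- This assumes that each COVID-19 replacement joins the group of the subject replaced, which the documents do not state. If both replacements were extra subjects in Group 3 or 6, the maximum would be 2 + 2 = 4.
- The two delayed subjects cannot contribute. Their latest allowable surgery dates (27 April and 02 May 2020) minus 45 days give last doses on 13 March and 18 March 2020. Any later surgery is at least 46 days after the last dose, so d is -46 or earlier and the listed day is -45 or earlier.

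Separately, any AE that starts the day before surgery is listed as Day 0, in any subject.

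Treatment-emergent status compares the onset date with the first injection (SAP 4.4.1.1), and AE duration uses start and end dates. Neither uses AE Onset Day, so neither changes.

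**The case against.** The strongest reply is that listings-only is inferred from silence. SAP 7.2 says outright that protocol deviations are not summarized, while 7.9.2 says nothing of the kind about AEs. SAP 6.1 has general rules for summarizing discrete data and for empty summary tables. SAP 4.4.1 sets up MedDRA coding, severity and causality. All this suggests that a summary was intended and a sentence left out. The shells in Module 2 may contain the table, and a silent SAP does not cancel the protocol.

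Part of this stands. An AE table may exist in Module 2, and the omission may well be a drafting slip. But silence is not all there is: Table 4 and Section 7.9 positively describe safety output as listings. If a summary was intended, 7.9.2 still needs the sentence that says so.

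The second reply is that the tension starts in Protocol 9.3. That is true, and it explains how the SAP came to read as it does. It does not override 9.3.2.1, which is the specific AE provision and asks for more than its neighbours do.

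The third reply is that the consequence is small: about 10 subjects, one or two planned per group, no hypotheses, and every AE listed. This also stands, and it limits the weight of the point. On AESIs, the injection-site sentence sits under the SAP's AESI heading, so the text is ambiguous and does not exclude those events.

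**Conclusion.** The concern holds. Module 1 specifies none of the four AE breakdowns in Protocol 9.3.2.1, bearing on a named secondary endpoint, while Section 8 declares no change. Two imputation rules are left without a stated use. This should be corrected, but no data are lost: every AE is listed, and the counts can be rebuilt by hand. The conclusion covers Module 1 only, because Module 2 was not available.

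The onset-day formula is wrong by one day on every date against the study's own day labels. It affects a listing label only. The clash between a Day -1 dosing-date event and the surgery-day label concerns 0 to 2 subjects if replacements are like for like, and at most 4 otherwise.

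The AESI wording is a clarification. Two of the protocol's three categories are expressly called AESIs in the SAP, and all three stand under that heading.

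**What to change.** 1. **SAP 7.9.2:** add the descriptive summary from Protocol 9.3.2.1 on the Safety Population: numbers of AEs and of subjects with AEs, by system organ class, preferred term, severity and causality. Identify treatment-emergent events in it. Section 9.3.2.1 does not itself ask for that, but the secondary endpoint does. If the sponsor prefers listings alone, declare the removal in Section 8, and delete the rules in 4.4.1.2 and 4.4.1.3 or state where they apply.
2. **SAP 6:** state that the absence of planned analyses means no inferential analyses, and that Protocol 9.3 is read the same way.
3. **SAP Table 5:** delete the added 1 from AE Onset Day. It then agrees with Study Day on all ten days checked.
4. **SAP 3.12.1:** align with Protocol 8.2.7 so that the AESI listing clearly includes injection-site events.

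The cost is one small table for about 10 subjects, or one sentence in Section 8, plus one clarifying sentence, one deleted term and one wording edit. If Module 2 already has the AE table, item 1 needs only the matching text in 7.9.2.
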